### 3.3 Pharmacokinetic endpoints

Pharmacokinetic analysis is not part of this SAP, it will be summarized in a separate document.

### 3.4 Pharmacodynamic endpoints

Pharmacodynamic analysis is not part of this SAP, it will be summarized in a separate document.

## 4 Study Design

### 4.1 Discussion of Study Design

This is the general summary of the study design in the 4 protocols, detailed design can be found in the individual study protocol for each of the 4 countries.

The design is a Phase Ib/II, open-label, dose-escalation and cohort expansion study to obtain a preliminary assessment of the safety, tolerability and efficacy of bemcentinib, a small molecule inhibitor of Axl kinase in patients with acute AML or high/intermediate (int-2) risk MDS. The study will be conducted at up to approximately 20 sites in Europe and the US and will be performed in approximately 102 evaluable patients with AML or MDS. Additional countries and sites may be added as required to meet the enrolment needs of the study.

Bemcentinib will be administered orally according to a daily schedule during continuous 21-day treatment cycles. During Cycle 1, Week 1 ONLY the first 3 doses of bemcentinib may serve as a 'loading' dose.

Dosing will consist of a loading dose of 200 mg administered on Days 1, 2 and 3 followed by a daily maintenance dose of 100 mg. This dose may be escalated as agreed by the SMC to a maximum daily loading dose of 400 mg on Days 1, 2 and 3 followed by a maximum daily maintenance dose of 200 mg.

Patients will be instructed to take bemcentinib on an empty stomach at a similar time each morning when they wake, or more than 2 hours after a light meal, with water. To maintain a fasted state, patients should be told not eat or drink anything other than water for at least 1 hour after taking the drug.

In Part A the study will follow a 3+3 design to explore the safety and tolerability of repeat dosing of bemcentinib, and to identify the MTD and/or RP2D. A minimum of 6-10 patients will be treated at the MTD and/or RP2D, as determined by the SMC. Depending upon the results of this phase of the study, the safety and efficacy of bemcentinib may be established in up to 4 disease-specific cohorts in Part B.

#### Part B1

Single agent bemcentinib will be administered to patients with AML who are unsuitable for intensive chemotherapy as a result of advanced age and or existing co-morbidities. In order to be eligible patients should have received at least one line of previous therapy.

#### Part B2

Bemcentinib will be administered in combination with cytarabine to patients with AML who are not suitable for intensive chemotherapy as a result of advanced age or existing co-morbidities.

#### Part B3

Bemcentinib will be administered in combination with decitabine to patients with AML who are not suitable for intensive chemotherapy as a result of advanced age or existing co-morbidities.

#### Part B4

Single agent bemcentinib will be administered to patients with intermediate (int-2) or high risk MDS according to the International Prognostic Scoring System (IPSS) Risk Stratification [Greenberg, 1997]. Patients must have received at least 1 prior treatment for their disease.

[figure not shown]
Prior treatment may include those patients who have received hypomethylating agents, decitabine or other approved treatments for MDS.

#### Part B5

Bemcentinib will be administered in combination with cytarabine in patients with AML who are unsuitable for intensive chemotherapy as a result of advanced age or existing co-

morbidity. Patients must have received at least one prior treatment for AML. Please refer to Figure 1 for an outline of the overall study design.

Figure 1: BGBC003 Study Design

### Phase I DLT Assessment Period

During the dose-escalation phase (Part A), safety, tolerability, PK, and preliminary clinical activity of BGB324 will be assessed, and the MTD established, in patients with AML who have received previous treatment with cytotoxic chemotherapy or a targeted or biologic agent (e.g. hypomethylating agent, tyrosine kinase inhibitor, antibody) or a gene expression modulator, such as a demethylating agent and have relapsed after or have been refractory to treatment with such prior therapy or in high risk MDS. Patients suitable for intensive chemotherapy should be in second or subsequent relapse or be refractory to at least two induction regimens. Patients receiving an allograft in first remission would be eligible at the time of relapse.

A loading dose (Cohort 1) of 200 mg administered on Cycle 1, Days 1, 2 and 3 followed by a daily maintenance dose of 100 mg during continuous 21-day treatment cycles will be evaluated. This dose may be escalated as agreed by the SMC to a maximum daily loading dose of 400 mg on Days 1, 2 and 3 followed by a maximum daily maintenance dose of 200 mg. At least three evaluable patients will be entered per cohort.(see Section 9 of the individuals protocols). At least three evaluable patients will be entered per cohort.

## Dose Escalation Scheme

Initially three patients will be recruited into Cohort 1 and will complete 1 cycle of treatment before a dose-escalation evaluation is made. A patient must receive all loading doses and miss no more than 3 standard doses in Cycle 1 in order to be considered as informative to support dose escalation, unless the missed doses are due to bemcentinib toxicity.

The decision to dose-escalate (or not) will be made by the SMC comprising a representative from each actively recruiting investigational site and a representative of the BerGenBio AS study team. Minutes of the SMC meeting will be recorded and circulated for final approval before being placed in the Trial Master File (TMF). The decision to dose escalate will be based upon the tolerability of bemcentinib observed at the previous dose level. Dose escalation will range between 25% and 50% of the previous dose according to the nature and severity of the toxicity observed.

Where dose escalation occurs, three patients will be recruited to the next Cohort (dose level) and will complete 1 cycle of treatment before a dose-escalation evaluation is made, as outlined above.

If one patient in a cohort experiences a DLT during Cycle 1, the cohort will be expanded to six patients. If two of three or two of six patients in a cohort experience DLT no further dose-escalation will take place and the dose below will be nominated as the MTD. If the starting dose exceeds the MTD, a lower dose may be explored if recommended by the SMC. Provided treatment with the starting dose is considered safe by the SMC according to DLT evaluation, dose escalation may proceed.

The maximum daily dose that may be explored in this study will be 400 mg.

If a patient withdraws or is withdrawn for reasons other than DLT prior to completing Cycle 1, the patient will be replaced for the purposes of toxicity evaluation.

## Dose Limiting Toxicity

DLT will be assessed during the first 3 weeks of treatment (Cycle 1) with bemcentinib, according to the National Cancer Institute (NCI) Common Terminology Criteria for Adverse Events (CTCAE) version 4, considered unrelated to leukemia progression or intercurrent illness, and defined as any of the following:

- CTCAE Grade 3 or 4 nausea, vomiting, or diarrhea that persists despite maximum prophylactic and supportive care
- Any other CTCAE Grade 3 or 4 non-hematological toxicity that is considered to be clinically significant and causally related to BGB324, excluding isolated changes in laboratory results if no clinical significance or no clinical sequelae and adequately improve within 7 days.
- Prolonged neutropenia with ANC < 500 and platelet count < 75000 after Day 42 from the start of treatment in the absence of residual leukemia
- Treatment discontinuation, inability to administer one or more BGB324 loading dose, or inability to administer three BGB324 maintenance doses as result of BGB324-related toxicity
- Any Ventricular Arrhythmia

**Part B:** Following SMC review of all treatment emergent safety and efficacy data from Part A, up to 14 evaluable patients (up to 20 evaluable patients in Part B5) will be recruited into four cohorts .

Depending upon the safety profile of BGB324 observed in Part A the initial starting dose in combination with cytarabine (Part B2) or decitabine (Part B3), may be reduced by a single dose level (i.e. MTD -1) which will be evaluated in at least three subjects before introduction of the MTD or RP2D identified in Part A. The bemcentinib dose level to be investigated in Part B2 and Part B3 will be dependent upon the MTD confirmed in Part A. A dose lower than 100 mg daily is not available. The Part B5 dose is based on the combination dose that was identified as safe and well tolerated in Part B2.

## 4.2 Study Treatment

Every patient enrolled in the study will receive bemcentinib. Patients enrolled in Part B2 and B5 will receive bemcentinib in combination with low dose cytarabine. Patients enrolled in Part B3 will receive bemcentinib in combination with decitabine. More detailed information for the treatment scheduled and administration are provided in section 12.1 of the individual protocols.

### 4.2.1 Bemcentinib

In Part A, the starting dose of bemcentinib (Cohort 1) will be 200 mg on Cycle 1, Days 1, 2 and 3 (loading dose), followed by a daily maintenance dose of 100 mg. In Part B depending upon the safety profile of bemcentinib observed in Part A the initial starting dose in combination with cytarabine (Part B2) or decitabine (Part B3) may be reduced by a single dose level (i.e. MTD -1) which will be evaluated in at least three patients in each cohort before the introduction of the MTD identified in Part A. The bemcentinib dose level to be investigated in Parts B2 and B3 will be dependent upon the MTD confirmed in Part A. A dose lower than 100 mg daily is not available.

The bemcentinib dose in Part B5 (combination with low dose cytarabine) will be 400 mg orally daily for the first 3 days of treatment (loading dose) and 200 mg orally daily thereafter (maintenance dose).

Patients receiving Formulation 2 will be instructed to take bemcentinib on an empty stomach at a similar time each morning when they wake, or more than 2 hours after a light meal, with water. To maintain a fasted state patients should be told not eat or drink anything other than water for at least 1 hour after taking the drug.

Patients will record their dosing at home in a dosing diary that will be reviewed regularly by the site staff. Patients will be instructed as to the importance of following the dosing instructions they have been provided with, and for maintaining an accurate and up to date dosing record. Patients will also be instructed to bring their dosing diary and all bemcentinib bottles, including unused and empty bottles, with them to each study visit. The site staff will record the amount of used and unused bemcentinib capsules at selected study visits.

### 4.2.2 Cytarabine (Part B2 and Part B5)

For Part B2, cytarabine will be administered subcutaneously according to standard practice (i.e. 20 mg/m^2 twice daily for 10 days followed by a rest period of <1 month according to persisting myelosuppression). Cytarabine should be administered approximately 30 minutes after the bemcentinib dose.

For Part B5, cytarabine will be administered at a dose of 20 mg subcutaneously twice daily for 10 days every 28 days. Cytarabine should be administered approximately 30 minutes after the bemcentinib dose.

If toxicity presents, then the cytarabine dose may be modified in accordance with the approved prescribing information or Summary of Product Characteristics (SmPC) and in accordance with local treatment guidelines.

#### 4.2.3 Decitabine

Decitabine will be administered per standard local practice up to a maximum dose of 20 mg/m^2 body surface area by intravenous infusion over one hour, repeated daily for five consecutive days (i.e. a total of five doses per treatment cycle).

The total daily dose must not exceed 20 mg/m^2 and the total dose per treatment cycle must not exceed 100 mg/m^2. The cycle should be repeated every four weeks depending on the patient's clinical response and observed toxicity. Decitabine should be administered within approximately 30 minutes of bemcentinib dose.

If toxicity presents, then the dose may be modified in accordance with the approved prescribing information or SmPC and in accordance with local treatment guidelines.

Both cytarabine and decitabine are considered to be standard of care for these patients and will not be supplied or reimbursed by BerGenBio ASA.

### 4.3 Study Schedule

The study period will consist of screening, treatment, Final Study Visit, and follow-up. The Final Study Visit will occur 28 days after the patient has discontinued study treatment. A detailed Schedule of Events can be found in the section 9.3 of the Norway, US and German study protocols and 9.2 of the Italian study protocol.

#### 4.3.1 Screening

Patient eligibility for the study will be determined within 14 days prior to the first dose of BGB324. Screening assessment will be conducted according to the schedule of events in section 11 of the protocol.

#### 4.3.2 Treatment

Eligible patients will visit the study site to receive study treatment and protocol-specified procedures according to the relevant Schedule of Events in the study protocol, Section 11. The treatment period will consist of continuous 21-day treatment cycles.

Patients will be intensively monitored throughout Day 1 to Day 4 inclusive of Cycle 1, and in addition will attend the clinic on Day 8, and Day 15.

Patients will attend the clinic once per week during Cycle 2 and then once per cycle thereafter. All patients will continue to receive bemcentinib or the combination for as long as, in the opinion of the investigator, they continue to derive clinical benefit. When there is unacceptable toxicity, confirmed disease progression in the absence of clinical benefit, death or withdrawal of consent, bemcentinib or combination treatment must be discontinued.

For patients in the combination arms (Part B2, B3 or B5), if treatment-related toxicity requires discontinuation, and the toxicity can be clearly assigned to one of the study treatments, the other study drug in the combination can be continued if it is safe to do so (investigator discretion) in the absence of disease progression or intolerable toxicity. The investigator may also decide to discontinue both study treatments at this time.

Patients with AML who are receiving bemcentinib monotherapy and who do not achieve an objective response after two cycles of treatment may start additional therapy with oral anti-metabolites (e.g. 6-mercaptopurine, hydroxyurea), or low dose cytarabine, or melphalan

administered at 50% of the institution's starting dose, which may be escalated in subsequent cycles according to tolerability.

#### 4.3.3 Final Study Visit

Patients will return to the study site for the Final Study Visit 28 days after permanent discontinuation of all study treatments.

#### 4.3.4 Follow Up

An AE will be monitored for 28 days after the last dose of BGB324, although only events considered to be related to treatment need to be recorded in the electronic Case Report Form (eCRF) between the last administration of BGB324 and the end of the 28 day follow up period. If BGB324-related toxicities continue beyond the follow up period, patients will be followed until all BGB324-related toxicities have resolved to  $\leq$ Grade 1, stabilised or returned to baseline. If necessary, follow up monitoring for AEs may be conducted over the telephone.

SAEs with a suspected relationship to BGB324 will be collected beyond the 28-day follow-up period until the event is resolved to  $\leq$  Grade 1, stabilized or returned to baseline.

All patients that have permanently discontinued study treatment for whatever reason must be followed for survival. The investigator or designee must confirm with the patient at the time of the Final Study Visit how the patient will be followed for survival (e.g. contact with family or health care provider). Survival follow-up must be conducted at least every 3 months by the investigator or designee and the date-of-death reported in the eCRF.

All subsequent anticancer therapy for AML or MDS must be reported in the eCRF.

#### 4.3.5 End of Study

Except in the case of early termination (Section 9.4), the end of the study is defined as the date when all patients have an OS event, unless the Sponsor terminates OS follow-up once all patients have discontinued study treatment. Should the last patient enrolled to the study be continuing to receive bemcentinib 52 weeks from their Cycle 1 Day 1, the Sponsor may choose to lock the data base to that point and prepare the clinical study report (CSR). Data collected as part of this study after this point, will be reported as an addendum to the CSR.

A final clinical study report will be prepared when the last patient has completed their Final Study Visit and the database is locked. The Statistical Analysis Plan (SAP) will be finalized and signed before database lock.

Patients will continue to be followed for suspected SAEs until these are resolved to  $\leq$  Grade 1, stabilized or returned to baseline. Refer to Section 15.2.2 for SAE reporting after the end of study.

### 4.4 Concomitant Medication and Procedures

All prescription, non-prescription, or over-the-counter medications including herbal remedies given to, or taken by, the patient at entry and during the study must be clearly documented in the eCRF.

The patients must be instructed that no additional medication will be allowed without the prior consent of the investigator. Any medication considered necessary for the patient's safety and well-being may be given at the discretion of the investigator. Hematopoietic growth factors may be administered for the treatment of AEs such as neutropenic infections but should not be used to maintain the dose intensity of bemcentinib in Part A. Patients who have evidence of treatment benefit after  $>1$  cycle of treatment in Part B may receive hematopoietic growth factors to maintain bemcentinib dosing.

Concurrent treatment with any agent known to cause QT prolongation and have a risk for Torsades de pointes is an exclusion criterion for the study. A comprehensive list of these prohibited medications is provided in the study protocol Appendix 3.

Treatment with any medication which is predominantly metabolized by CYP3A4 and has a narrow therapeutic index is also excluded (see Appendix 4 in study protocol for details of CYP3A4 substrates). Patients being treated with antacid histamine receptor 2 inhibitors or proton pump inhibitors within 3 days of administration of bemcentinib will be excluded. The Investigator may initiate rescue treatment with these medications in the evening for symptomatic relief following one week's treatment with bemcentinib.

## 4.5 Study Analysis Populations

### 4.5.1 Enrolled Population

The Enrolled Population will include all patients who have signed the ICF and enrolled into the study (Enrolment date being defined as the date of the first protocol-defined screening procedure).

### 4.5.2 Safety Analysis Population

The Safety analysis population will be defined as all enrolled patients who receive at least one dose of bemcentinib. The Safety analysis population will be analysed by dose group or combination in Part B.

Patients enrolled to Part A who meet the eligibility criteria for Part B1 and who receive the MTD and/or RP2D, may contribute to the Part B1 analysis.

### 4.5.3 Efficacy Analysis Population

The Efficacy Analysis Population will include all from Safety Analysis Population that,

- ✓ Meet key eligibility criteria, have assessable disease at baseline and have at least one post-baseline response assessment
- ✓ Have received >1 dose of bemcentinib (and combination agent in Part B2, B3 and B5)

Any patient who continues treatment with bemcentinib beyond confirmed disease progression will be followed for the same safety and efficacy assessments as for all other patients enrolled into the study until they are withdrawn from the study as defined in protocol section 13.

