FOLLOW UP:	
AEs will be monitored for 28 days after the last dose of study treatment. If bemcentinib-related toxicities continue beyond the follow up period, patients will be followed until all bemcentinib-related toxicities have resolved to ≤Grade 1 or less, stabilized or returned to baseline. Follow up monitoring for AEs may be conducted over the telephone. Serious adverse events (SAEs) with a suspected relationship to bemcentinib will be collected indefinitely.
 
The study will be completed when all patients have completed their final study visit.
 
All patients will be followed for survival after they have permanently discontinued from study treatment at ≤ 3 monthly intervals by the site. Subsequent anticancer therapies for AML or MDS must be collected in the electronic case report form (eCRF).
 
The study will be completed when all patients have an OS event, unless the Sponsor terminates OS follow-up once all patients have discontinued study treatment.

STATISTICAL METHODS	
As this is an early study of bemcentinib only descriptive analysis will be performed on safety data. Preliminary statistical analysis will be performed on objective response rates in Part B.
 
Safety:
 
All safety and tolerability assessments will be based on the safety analysis set (all patients who have received at least one dose of study medication).
 
Efficacy:
 
Efficacy assessments will be based on the safety analysis set.

	
Note: patients treated with bemcentinib beyond disease progression will be followed for the same safety and efficacy assessments as for all other patients enrolled into the study until they are withdrawn from the study. The data for patients treated beyond progression will be presented in both a combined output (with all patients) and also a separate output (to reflect a new period of analysis). All data collected will be included in the study CSR.
 
Pharmacokinetics:
 
Individual and mean bemcentinib plasma concentration-time data will be presented in tabular and graphical form. PK parameters for bemcentinib will be derived from an appropriate PK model will be determined using a non-compartmental analysis. Full details of the PK analysis will be presented in a PK Analysis Plan.
 
Pharmacodynamics:
 
Pharmacodynamic data will be listed and summarized by dose cohort and time point as appropriate.

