16.5. Efficacy

16.5.1. Analysis Population

The Efficacy Analysis Population will include all subjects who receive >1 dose of bemcentinib (Full Analysis Set).

Any patient who continues treatment with bemcentinib beyond confirmed disease progression will be followed for efficacy assessments (hematology testing, physical examinations and bone marrow biopsy, if clinically indicated), as defined in protocol section 13.

For the Per Protocol analysis set, the population will be defined as follows:

Patients that

- Meet key eligibility criteria, have assessable disease at baseline and have at least one post-baseline response assessment
- Have received >1 dose of bemcentinib (and combination agent in Part B2, B3 and B5)

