Partial Remission (PR)	All CR criteria met if abnormal before treatment except for: 
 • Myeloblasts decrease by 50% or more over pretreatment value but still >5%, or • Less advanced FAB or IPPS category compared to pretreatment value 	Hematologic improvement	Absolute values must last at least 6 weeks.
Marrow CR	≤5% myeloblasts and decrease by ≥50% over pretreatment value	If hematologic improved, these should be noted in addition to marrow CR (see Category B).	
Stable Disease (SD)	Failure to achieve at least PR, but no evidence of PD for at least 3 treatment cycles.		
Progressive Disease (PD)	
 • For patients with less than 5% myeloblasts: a 50% or more increase in myeloblasts to more than 5% myeloblasts. • For patients with 5% to 10% myeloblasts: a 50% or more increase to more than 10% myeloblasts. 	Myeloblast increase plus at least one of the following: 
 • ≥50% decrease in ANC or platelets • Reduction in Hb by ≥2g/dL • Transfusion dependence. 	Death during treatment

	
 For patients with 10% to 20% myeloblasts: a 50% or more increase to more than 20% myeloblasts. For patients with 20% to 30% myeloblasts: a 50% or more increase to more than 30% myeloblasts. 		
Relapse after CR or PR	
Relapse is characterized by at least one of the following:
 
 Return to pretreatment myeloblasts percentage ≥50% decrease in ANC or platelets 
Reduction in Hb by ≥2g/dL or transfusion dependence.
		
Disease transformation	
Transformation to AML (30% or more blasts).
		
Category B: Hematologic Improvement (HI)			
	Hematopoietic Lineage	Response Criteria	Definition ^a
	Erythroid (HI-E)	Major response	For patients with pretreatment Hb<11 g/dL, greater than 2 g/dL increase in Hb; for RBC transfusion-dependent patients, transfusion independence.
		Minor response	For patients with pretreatment Hb <11 g/dL, 1 to 2 g/dL increase in Hb; for RBC transfusion-dependent patients, 50% decrease in transfusion requirements.
	Platelet (HI-P)	Major response	For patients with pretreatment PLT counts of <100 x 10 ⁹ /L or 100,000/µL, an absolute increase of 30 x 10 ⁹ /L or 30,000/µL or more; for PLT transfusion-dependent patients, stabilization of PLT counts and PLT transfusion independence.

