### 4.5.1 Per protocol Analysis Population

No per protocol population will be analysed in this study.

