## 5.14 Changes in Conduct or Planned Analyses from the Protocol

Following are the changes in analyses from those defined in the protocol:

- Population of analysis is updated to match with the usual definition in clinical trials. In the protocol, safety population and efficacy population have the same definition and per protocol population definition is the typically definition of efficacy population. Then, the efficacy population is updated with definition of per protocol and it is decided that no per protocol analysis will be handled.
- The exploratory objective "To explore the correlation between baseline biomarker levels and clinical endpoints". Biomarker data will be analyzed in exploratory analyses not in scope of this SAP so this analysis will be presented within biomarker analysis.

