## 6.7 Appendix

### 6.7.1 Definitions of End Points for Clinical Trials in AML by Cheson & all 2003.

Outcome	Response Category	Point of Measurement	Definition
Overall survival	All patients	Entry onto trial	Death from any cause
Relapse-free survival	CR	Leukemia-free state	Disease relapse or patient death from any cause
NOTE. Complete blood counts should be evaluated at least monthly, or more often if clinically indicated, to establish the durability of responses.			
Abbreviations: AML, acute myelogenous leukemia; CR, complete remission.

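### Part B OS and EFS are limited to patients with a post-baseline response assessment, so treated AML patients who die unassessed are in neither, and no all-treated ORR, EFS or OS remains

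*SAP*

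**What the plan says.** **Protocol.** The synopsis states: "Efficacy assessments will be based on the safety analysis set". Section 16.5.1 states: "The Efficacy Analysis Population will include all subjects who receive >1 dose of bemcentinib (Full Analysis Set"). The set that requires an assessment is defined separately there, as the Per Protocol set.

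**SAP.** Section 4.5.3 moves that condition into the Efficacy Analysis Population: "Meet key eligibility criteria, have assessable disease at baseline and have at least one post-baseline response assessment". It also requires more than one dose of bemcentinib, and the combination agent in B2, B3 and B5. Section 5.14 explains the change. It first notes "In the protocol, safety population and efficacy population have the same definition", then says "Then, the efficacy population is updated with definition of per protocol and it is decided that no per protocol analysis will be handled". Its second section numbered 4.5.1 confirms "No per protocol population will be analysed in this study".

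**Where the set is used.** SAP 5.1 applies it to all efficacy analyses. Sections 6.3.2 and 6.5 attach it to the six ORR tables (Parts A and B), to the Part B OS and EFS tables, and to the six OS and EFS Kaplan-Meier figures.

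**Timing.** SAP 5.7 runs OS and EFS from first intake of bemcentinib and counts death as an event in both. Protocol 13.4 places the first scheduled response assessment at Cycle 2 Day 1, which is Day 22 with 21-day cycles.

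**The concern.** Membership of the OS and EFS analysis set depends on something that happens after the clock has started. A patient who is treated, dies in the first three weeks and has no recorded assessment has had an OS and EFS event, yet contributes to neither curve. Leaving out early events makes both endpoints look better than they were in treated patients. The SAP expects such deaths: section 5.8.1.1 flags deaths in the first four weeks, but only in a listing.

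The second part concerns ORR. The protocol's efficacy set was treated patients, and after SAP 5.14 no ORR on that set is planned. A reader of the study report would have no all-treated median, curve or response rate for any Part B cohort.

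**Working it through.** **1. Can anything bring an unassessed AML death back?** Nothing in SAP 5.7 does. AML progression in protocol Appendix 5 is defined by blasts and extramedullary disease, not by death. The early-death row in the RFS table does not help, because RFS covers responders only. For MDS (B4) the answer is open: the PD row in protocol Appendix 6 includes "Death during treatment", and the documents do not say whether a death recorded as PD counts as a response assessment.

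**2. Scenario for OS.** The documents give no early-death rate, so exponential survival and the true median m are assumptions.

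- Time to first scheduled assessment: L = 21/30.4375 = 0.690 months
- Hazard: λ = ln 2 / m
- Share dying before Day 22: s = 1 − exp(−λL)
- Median after excluding a fraction f of those deaths: −ln[0.5(1 − f·s)]/λ, which equals m + L when f = 1

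| True median (months) | s | Median if all unassessed | Median if half unassessed |
|---|---|---|---|
| 3 | 14.7% | 3.69 | 3.33 |
| 4 | 11.3% | 4.69 | 4.33 |
| 6 | 7.7% | 6.69 | 6.34 |

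The rise is 0.69 months if all are unassessed and about 0.33 months if half are.

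**3. Scenario in patients.** The caps of 14 (B1 to B4) and 20 (B5) in protocol 16.9 and SAP 4.9 count evaluable patients. The AML cohorts sum to 14 + 14 + 14 + 20 = 62 evaluable. If early deaths are the only exclusions, treated = 62/(1 − s):

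- m = 3: 62/0.8526 = 72.7 treated, 10.7 lost
- m = 4: 62/0.8873 = 69.9 treated, 7.9 lost
- m = 6: 62/0.9234 = 67.1 treated, 5.1 lost

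**4. Net direction.** Section 4.5.3 also removes patients who are ineligible, not assessable at baseline, without more than one dose, or without the combination agent. Some of these may be long survivors. If a fraction d is removed below the true median and the same fraction above it, 0.5 − d remains on each side and the median does not move. In the 4-month case, dropping the 11.3% of early deaths and another 11.3% who outlive 4 months returns 4.0.

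**5. ORR.** The plan's stated power reproduces. With a null rate of 5%, an alternative of 20% and size 0.2, the exact binomial rule at 14 evaluable is at least 2 responders (size 0.153, power 0.802). At 20 evaluable it is at least 3 (size 0.075, power 0.794). Now take 2 responders and add unassessed treated patients as non-responders, with P = 1 − 0.95^n − n(0.05)(0.95)^(n−1):

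- n = 14: P = 0.153
- n = 15: P = 0.171
- n = 16: P = 0.189
- n = 17: P = 0.208

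The same 2 responses stop meeting P < 0.2 once three unassessed patients are counted.

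**The case against.** **The change is disclosed.** SAP 5.14 states it openly and gives a reason, that the new definition is the usual one. That stands, and nothing is concealed. The reason given does not address endpoints whose clock starts at first dose.

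**The trial is sized in evaluable patients.** So it is, and SAP 3.2 introduces the AML endpoints as measured in evaluable patients. A reader might infer that the response-evaluable ORR is itself an error. The documents do not support that: it fits the sample-size basis. The ORR point is only that the protocol's all-treated figure has gone.

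**Protocol 16.5.1 prints more than one dose, while the synopsis safety set needs only one.** This is true, but SAP 5.14 itself reads the two protocol sets as the same, so all-treated is a fair reading.

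**The scenarios may be too severe.** This stands. Protocol 13.4 allows assessments when clinically indicated, blasts are counted in Cycle 1 hematology, and AML progression can rest on peripheral blasts. Some early deaths may therefore have an assessment on record. The all-unassessed column is an upper bound for each assumed median, and the half case is arbitrary.

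**Much of the accounting already exists.** SAP 5.3 reports treated patients by analysis population, Listing 16.2.3 names those excluded from efficacy, deaths are listed with time from first intake, and survival follow-up is listed for the Safety Population. This also stands, but listings give no all-treated estimate.

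**SAP 6.7.1 can be read either way.** The table headed "Definitions of End Points for Clinical Trials in AML" gives OS for all patients, and a reader might infer a direct contradiction. The entry sits in the response-category column and may mean only that OS is defined whatever the response, so it is weak support.

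**Conclusion.** The point holds for Part B AML OS and EFS: a treated patient who dies with no recorded assessment is missing from both, and this omission biases both upward. For B4 it depends on how a death recorded as PD is classed. Separately, the protocol's all-treated efficacy analysis was replaced, and no all-treated ORR, EFS or OS was kept.

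The size is not known. Under exponential survival with true medians of 3 to 6 months, the OS median would rise by at most 0.69 months from this omission, and by about half that if half the early deaths are unassessed.

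A reader might go further and infer that the reported OS and EFS will be too favourable overall. The documents do not support that, because the other 4.5.3 conditions can also remove survivors and the net effect is undetermined. It would equally be wrong to assume that having an assessment guarantees inclusion.

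This should be fixed but does not undermine the trial. Protocol 16.5.2 calls efficacy essentially exploratory, and its P < 0.2 rule concerns ORR only.

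**What to change.** - **OS and EFS population.** Use the Safety Analysis Population (SAP 4.5.2).
- **EFS summary.** In Table 14.2.3.1, replace the raw mean, median, minimum and maximum with Kaplan-Meier estimates (events, censored, median, 95% CI), as SAP 5.7 already does for OS. Otherwise a patient censored at first intake enters the table as a 1-day duration.
- **EFS rule for patients with no post-baseline assessment.** Both existing censoring rows need an assessment date that these patients lack. Count death as an event on its date. Censor at first intake those who are alive without an event or who started new anticancer treatment first, in line with those rows. A death after new treatment then remains uncounted in EFS, as under the present rule, but is counted in OS.
- **ORR and DCR.** Report them on all treated patients, with unassessed patients as non-responders, beside the response-evaluable figures on the 4.5.3 set.
- **Accounting.** Add a count by reason for exclusion, per cohort, to the disposition table and Listing 16.2.3. State how a B4 death recorded as PD is treated.

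The cost is SAP text, one EFS rule, relabelling and re-running 2 tables, 6 figures and the OS and EFS listings, and a few extra ORR and DCR tables. Protocol 9.3.4 already requires survival follow-up of every patient who stops treatment, so no new data are needed. The downside is two ORR denominators to explain and possibly less favourable figures.
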